6.1.2 Secondary Objective(s)

- 2) To compare the differences in JIA Core Outcomes [15] for intravenous methylprednisolone versus oral prednisolone for the following domains:
 - a. Pain
 - b. Function
 - c. Health-related Quality of Life (HRQOL)
- 3) To assess the effectiveness of intravenous versus oral corticosteroids in minimising the need for additional treatments including all corticosteroid routes and additional disease-modifying anti-rheumatic drugs (DMARDs)/biologics.
- 4) To evaluate short/medium term safety and tolerability of IV versus oral corticosteroids, with regards to adverse reactions, serious adverse events, laboratory assessments and paediatric glucocorticoid toxicity index (pGTI).
- 5) To determine if a dose response relationship can be identified in the efficacy/adverse responses to corticosteroids across all participants by secondary analysis, normalising corticosteroids received for dose, bioavailability and potency using previously published data.

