9.10.6 Blinding

This is an open label trial with no blinding requirements.

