11 SAFETY REPORTING

Safety reporting in clinical trials is a legal and ethical requirement and it is imperative that all applicable requirements detailed here are followed during the trial.

For the purposes of this study, Adverse Reactions (AR) related to the interventions, IV methylprednisolone and oral prednisolone and JIA-related Uveitis and **all** Serious Adverse Events (SAEs) are reportable.

ARs will be collected at 6 weeks and 12 weeks **only** due to the short half-life of corticosteroids and that most adverse reactions occur whilst on or shortly after stopping corticosteroids.

All Serious Adverse Events (SAEs) will be recorded throughout the study and must be reported immediately (and within 24 hours of knowledge of the event) by entry into the trial database and signed off by the PI.

This includes SAEs related to IMPs and Non-Investigational Medicinal Products (NIMPs). Any trial specific SAE reporting exceptions are detailed in section 11.4.

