11.6 Assessment of “Causality” - Relationship to Trial Treatment/Intervention

The assessment of the causality should be made by the investigator responsible for the care of the participant using the definitions in the table below. Assessment should be made against the IMP or comparator administered to a participant.

Table 3: Definitions of Causality

Relationship	Description
Unrelated	There is no evidence of any causal relationship. N.B. An alternative cause for the AE should be given.
Unlikely	There is little evidence to suggest there is a causal relationship (e.g. the event did not occur within a reasonable time after administration of the trial medication). There is another reasonable explanation for the event (e.g. the participant’s clinical condition, other concomitant treatment).
Possibly	There is some evidence to suggest a causal relationship (e.g. because the event occurs within a reasonable time after administration of the trial medication). However, the influence of other factors may have contributed to the event (e.g. the participant’s clinical condition, other concomitant treatments).
Probably	There is evidence to suggest a causal relationship and the influence of other factors is unlikely.
Almost certainly	There is clear evidence to suggest a causal relationship and other possible contributing factors can be ruled out.

Events that are assessed as being possibly, probably or almost certainly related will be classed as “Related” (i.e. having a reasonable possibility of being a causal relationship), and events assessed as unrelated or unlikely will be classed as “Unrelated” (i.e. having no reasonable possibility of being related).

Assessment of causality should be made based on known safety profiles of the IMPs in question (e.g. SmPC) or of other drugs in the same class.

In the case of discrepant views on causality between the treating investigator and others, **the causality assessment of the treating investigator will never be downgraded** and the MHRA & REC will be informed of both points of view.

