11.9 Notes on Safety Event Recording

The following events must be recorded for the purposes of the trial:

- An exacerbation of a pre-existing illness
- An increase in frequency or intensity of a pre-existing episodic event/condition
- A condition (even though it may have been present prior to the start of the trial) detected after trial drug administration
- Continuous persistent disease or symptoms present at baseline that worsens following the administration of the trial treatment
- Laboratory abnormalities that require clinical intervention or further investigation (unless they are associated with an already reported clinical event)

- Abnormalities in physiological testing or physical examination that require further investigation or clinical intervention
- Injury or accidents
- Pregnancy (See section 11.10 for more details)

Do not record:

- Non-related Adverse Events
- Medical or surgical procedures - the condition which leads to the procedure is the adverse event
- Pre-existing disease or conditions present before treatment that do not worsen
- Situations where an untoward medical occurrence has occurred e.g. cosmetic elective surgery
- Overdose of medication **without signs or symptoms**
- The disease being treated or associated symptoms/signs unless more severe than expected for the participant's condition

*N.B. If overdose occurred **with** resulting signs and symptoms that meet the protocol criteria for SAE (i.e., requiring hospitalisation) then they should be reported accordingly (see section 11.4 for more information) and the overdose highlighted to the LCTC team.

The events above do not need recording as the trial is considered low risk. Both the IMP and Comparator are given in standard care for new onset pJIA. This is documented in the Risk Assessment.

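### Non-serious events count as adverse reactions only if an unblinded investigator calls them related, partly on time since dosing, so the 3-day IV and 6-week oral courses would be expected to give unequal counts even at equal background event rates

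*Protocol*

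**What the plan says.** **What is compared.** Objective 4 in section 6.1.2 begins "To evaluate short/medium term safety and tolerability of IV versus oral corticosteroids, with regards to adverse reactions, serious adverse events" and goes on to name laboratory assessments and the pGTI. In the outcome tables (sections 3 and 6.2), pGTI is the only listed outcome mapped to objective 4.

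**Who decides relatedness.** Section 9.10.6: "This is an open label trial with no blinding requirements". Section 11.6: "The assessment of the causality should be made by the investigator responsible for the care of the participant". If others disagree, "the causality assessment of the treating investigator will never be downgraded".

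**How it is decided.** Table 3 in section 11.6 uses timing as an example in both directions. An event may be possibly related "because the event occurs within a reasonable time after administration of the trial medication", and unlikely to be related if "the event did not occur within a reasonable time after administration of the trial medication". No number of days is attached. Possibly, probably and almost certainly are classed as related; unlikely and unrelated are classed as unrelated. The same section also refers to alternative explanations and to known safety profiles.

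**What is recorded.** Section 11 makes adverse reactions, JIA-related uveitis and all SAEs reportable. It collects adverse reactions at weeks 6 and 12 only, on the ground that "most adverse reactions occur whilst on or shortly after stopping corticosteroids". Section 11.2 says only serious adverse events are reportable. Section 11.9 puts "Non-related Adverse Events" on its do-not-record list. Section 11.12.1 instead makes the PI responsible for recording every adverse event, related or not.

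**Course length.** Section 3 gives a 3-day course for IV and a 6-week course for oral.

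**The concern.** The timing criterion interacts with the design. A mild infection or stomach upset at week 4 falls on treatment in an oral participant but more than three weeks after the last dose in an IV participant. An investigator applying Table 3 in good faith, and knowing the arm, has a documented reason to call the first possibly related and the second unlikely. The remark in section 11 about when reactions occur points towards a short lag.

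If section 11.9 is followed, the second event never enters the database, and no later analysis can recover it. The adverse-reaction count would then partly measure how long each course lasts. A real but delayed reaction to IV would be among the events most easily lost. At stake is the adverse-reaction component of the safety comparison; the primary outcome and the sample size are not touched.

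**Working it through.** The protocol states no adverse event rate, lag or safety power, so there is no figure of its own to reproduce here. The only design figure needed is the total of 130 (section 12.1.1), which at 1:1 allocation is 65 per arm.

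**Inputs from the protocol**
- Dosing: 3 days IV; 6 weeks = 42 days oral (section 3).
- Window: first dose to the week-12 visit, taken as 84 days in both arms (sections 11 and 11.8). This ignores visit windows and the delay of up to a week in starting treatment.

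**Assumptions, not in the protocol**
- An event is called related if it starts on treatment or within L days of the last dose, and unrelated otherwise.
- The background rate is constant and equal in both arms: 0.25, 0.5 or 1.0 non-serious events per participant over the 84 days.
- There is no true difference in harm.

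**Step 1: countable days.** IV = min(3 + L, 84); oral = min(42 + L, 84).

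| L (days) | Oral | IV | Ratio |
|---|---|---|---|
| 7 | 49 | 10 | 4.9 |
| 14 | 56 | 17 | 3.3 |
| 28 | 70 | 31 | 2.3 |
| 42 | 84 | 45 | 1.9 |
| 56 | 84 | 59 | 1.4 |
| 81 | 84 | 84 | 1.0 |

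**Step 2: participants with at least one recorded reaction.** P = 1 − exp(−rate × days / 84). At 0.5 events and L = 14, IV is 1 − exp(−0.5 × 17/84) = 9.6% and oral is 1 − exp(−0.5 × 56/84) = 28.3%, a risk ratio of 3.0.

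**Step 3: chance of a nominally significant false difference.** This uses a two-sided 5% comparison of two proportions with 65 per arm.

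| L (days) | IV v oral at 0.5 events | Risk ratio | Chance at 0.5 | Chance, 0.25 to 1.0 |
|---|---|---|---|---|
| 7 | 5.8% v 25.3% | 4.4 | 88% | 60–99% |
| 14 | 9.6% v 28.3% | 3.0 | 78% | 50–96% |
| 28 | 16.8% v 34.1% | 2.0 | 62% | 38–85% |
| 42 | 23.5% v 39.3% | 1.7 | 49% | 30–70% |

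With rarer events the chance falls. At 0.05 events per month (30.4 days), Fisher's exact test gives about 17% at L = 14 and 12% at L = 42.

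**Step 4: without the filter.** If all non-serious events over the 84 days count, both arms have the same expected proportion: 22.1%, 39.3% or 63.2% at 0.25, 0.5 or 1.0 events. The expected risk ratio is 1.00.

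**The case against.** **Scope.** A reader might infer that the whole tolerability comparison passes through this filter. The documents do not support that. SAEs are recorded whatever their cause (section 11), pGTI is scored at fixed visits in both arms (section 10.7.10), and laboratory assessments as a component of objective 4 do not depend on a causality call. This stands and limits the point to non-serious adverse reactions. It does not remove it, because objective 4 names adverse reactions separately from pGTI.

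**Timing is not a rule.** It is an example in Table 3, beside alternative explanations and known safety profiles. All participants are prescribed methotrexate (section 9.10.3), which offers another explanation in either arm. So it cannot be said that a week-4 event on IV will be called unlikely, only that Table 3 gives a reason to do so. A safety profile says what corticosteroids can cause; timing still helps decide whether this course did.

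**Section 11.12.1 points the other way.** A site following it would record unrelated events too, so loss at data capture is not certain. It depends on which section a site follows. Even with full recording, a comparison restricted to events judged related would still carry the same dependence on arm.

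**The size is assumed.** The model is all-or-nothing around L, the rates are illustrative, and section 12.4 specifies no test for adverse reactions in particular. This also stands: no single percentage should be quoted as the bias.

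**Limited recording is deliberate.** Section 11.9 justifies it by low risk. That is a fair reason to limit workload, but not to let the limit fall unequally on the arms.

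**Conclusion.** The point holds for the non-serious adverse-reaction component of objective 4. With equal background rates, more adverse reactions would be expected on oral, provided investigators give weight to timing and the lag they apply is shorter than about 81 days. The direction follows from 3 against 42 days of dosing. The size rests on the lag and event rate, neither of which the protocol gives: countable days run from 4.9:1 at a 7-day lag to 1.9:1 at 42 days, and the chance of a spurious significant difference ranges from about 12% to 99% over the lags of 7 to 42 days and the rates tried.

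The recording instructions in sections 11, 11.2 and 11.9 contradict section 11.12.1 and must be reconciled. Resolving them towards section 11.9 would build in the arm-dependent filter; resolving them towards section 11.12.1 would remove it at data capture. The correction is worth making before data accrue, because events that were never recorded cannot be recovered.

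**What to change.** 1. Reconcile sections 11, 11.2, 11.9 and 11.12.1 so that, from first dose to the week-12 visit, non-serious adverse events are recorded in both arms irrespective of causality. To limit workload, this could be a fixed list of corticosteroid effects drawn from SmPC section 4.8 (already the reference in section 11.7) that pGTI does not already capture, asked identically in both arms at weeks 6 and 12.
2. Base the between-arm comparison for objective 4 on these all-cause events, together with SAEs, laboratory assessments and pGTI.
3. Keep the investigator's causality judgement for SAR and SUSAR classification, and report investigator-attributed reactions descriptively only.

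**Cost.** Wording changes in section 11 and its subsections, and some extra lines on the week-6 and week-12 CRFs; less if the fixed list is used. No new visits or participants are needed, and no dose or treatment rule changes. Open-label ascertainment bias would remain, since families and staff still know the arm.

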11.7 Assessment of “Expectedness”

Assessments of expectedness are the Sponsor’s responsibility and are delegated to the LCTC and Medical Reviewer. There is no requirement for a reporting investigator to assess expectedness.

An event will be considered unexpected if it is not listed within the relevant document as detailed in the table below, which is current and approved for the trial at the time of the event’s onset.

Intervention	Document to be used for expectedness assessment	Relevant section to be used for expectedness assessment
Brand name: Solu-Medrone Manufacturer: Pfizer Active Substance: Methylprednisolone Sodium Succinate Dose: 1g Formulation: Powder for injection	SmPC	Section 4.8
Brand name: Prednisolone Manufacturer: Wockhardt UK Ltd Active substance: Prednisolone Dose: 1mg Formulation: Tablet	SmPC	Section 4.8

Side-effects of the trial interventions that are listed in the SmPCs will be regarded as expected.

The nature, severity, or frequency of the event should be considered – if this is not consistent with that described for the type of event in the RSI, the event will be assessed as unexpected. Fatal or life-threatening events related to the IMP/Intervention by nature, are deemed unexpected (unless specified in the RSI as such).

11.8 Time Period for Active Monitoring of Safety Events

Active monitoring of safety events experienced by trial participants will be from the period of IMP administration to last dose of IMP and up to their 12 weeks follow-up visit.

IMPORTANT: Any serious adverse event occurring in a trial participant after the end of the “active monitoring” period must continue to be reported by sites to the LCTC if the PI becomes aware of them. Reporting should be in accordance with the timeframes and procedures described in section 11.12.

11.9 Notes on Safety Event Recording

The following events must be recorded for the purposes of the trial:

- An exacerbation of a pre-existing illness
- An increase in frequency or intensity of a pre-existing episodic event/condition
- A condition (even though it may have been present prior to the start of the trial) detected after trial drug administration
- Continuous persistent disease or symptoms present at baseline that worsens following the administration of the trial treatment
- Laboratory abnormalities that require clinical intervention or further investigation (unless they are associated with an already reported clinical event)

- Abnormalities in physiological testing or physical examination that require further investigation or clinical intervention
- Injury or accidents
- Pregnancy (See section 11.10 for more details)

Do not record:

- Non-related Adverse Events
- Medical or surgical procedures - the condition which leads to the procedure is the adverse event
- Pre-existing disease or conditions present before treatment that do not worsen
- Situations where an untoward medical occurrence has occurred e.g. cosmetic elective surgery
- Overdose of medication **without signs or symptoms**
- The disease being treated or associated symptoms/signs unless more severe than expected for the participant's condition

*N.B. If overdose occurred **with** resulting signs and symptoms that meet the protocol criteria for SAE (i.e., requiring hospitalisation) then they should be reported accordingly (see section 11.4 for more information) and the overdose highlighted to the LCTC team.

The events above do not need recording as the trial is considered low risk. Both the IMP and Comparator are given in standard care for new onset pJIA. This is documented in the Risk Assessment.

11.10 Reporting of Pregnancy

[figure not shown]
Pregnancy, or the pregnancy of a partner occurring whilst participating in the trial, is not considered an SAE, however, a congenital anomaly or birth defect is. Other cases (e.g. termination of pregnancy without information on congenital malformation, and reports of pregnancy exposure without outcome data) should not normally be reported as such. When pregnancy occurs in a trial, either in a female participant or the female partner of a male participant, this should be followed up until at least the end of pregnancy, whether that is a live birth, abortion etc. If pregnancy occurs within the active monitoring period described in section 11.8, this must be reported via the database to the LCTC, within 24 hours of the research team becoming aware. All pregnancies and outcomes reported to LCTC will be notified to the trial Sponsor and monitored by trial oversight committees.

11.11 Notification of Deaths

If the research team become aware of the death of a participant (whether related to the trial or not) this should be notified reported via the database to the LCTC within 24 hours of becoming aware. Deaths occurring within the active monitoring period described in section 11.8 are reportable.

11.12 Reporting Procedures

All safety events which are recorded for the trial should be reported following the procedures detailed below. The occurrence of a safety event may come to the attention of research staff during routine trial visits, from the participant's notes, directly from the participant or by other means. Note that reporting procedures vary dependent on the nature of the incident (i.e. SAEs are to be reported to LCTC in an expedited manner). Any questions concerning safety reporting should be directed to the LCTC in the first instance. A flowchart is given below as an overview of reporting procedures for different types of safety events.

11.12.1 Site Responsibilities

Initial Reports

In addition to below requirements to report to the LCTC, safety events should also be reported to the site R&D team in accordance with local policy.

The site PI is responsible for ensuring that all adverse events (whether or not assessed as serious / related / expected) which the local research team becomes aware of are recorded on CRFs for trial purposes and reported to LCTC. It is the responsibility of the PI/Co-PI as recorded on the Delegation Log (medically qualified person) to assess the seriousness and causality of events.

All adverse events should be recorded in the database within 7 days of the site becoming aware of the event.

Events which are assessed as “serious” must **also** be recorded in the database **immediately and in no circumstances later than 24 hours from becoming aware**.

The assessments of seriousness and causality must be performed by an appropriately authorised medically qualified doctor. The following is considered the regulatory minimum reporting information and must be provided in initial reports:

- Participant study number
- Study site identifier and name of reporting site staff member
- Description of the event, including date of onset
- For CTIMPs: Suspect IMP
- Seriousness assessment
- Causality assessment

N.B. In the absence of a delegated medically qualified doctor the SAE CRF must be assessed by an alternative member of the research site trial team and submitted to the LCTC. As soon as possible thereafter the responsible investigator should check the SAE and make amendments as appropriate. The initial report shall be followed by detailed follow-up reports.

Follow-up Reports

All reportable adverse events should be followed until satisfactory resolution or until the investigator responsible for the care of the participant deems the event to be chronic or the patient to be stable. Where additional information on a SAE is received by site this must be entered into the database within 24 hours of becoming aware of the information.

Sites must respond to and clarify any queries raised on any reported SAEs and report any additional information as and when it becomes available through to the resolution of the event.

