10.7.8 Safety Assessments

An assessment of adverse reactions and serious adverse events will be undertaken at each study visit from baseline to the last trial visit. These reviews will be carried out by the PI or other delegated staff member conducting the visit. Requirements for adverse event reporting are detailed fully in Section 11.

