11.2 Adverse Events

Only adverse events that meet the definition of seriousness are reportable see section 11.3

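### The protocol gives sites conflicting rules on which non-serious events to record and until when, which weakens the adverse-reaction comparison in objective 4

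*Protocol*

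**What the plan says.** **Which events.**

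- The opening of section 11 makes three classes reportable: adverse reactions to the two steroid regimens, JIA-related uveitis, and all serious adverse events.
- Section 11.2 says "Only adverse events that meet the definition of seriousness are reportable" and makes no exception for reactions.
- Section 11.9 has a list of items that sites must not record, and "Non-related Adverse Events" stands on it. The same section has a list of items that must be recorded. That list includes injuries and accidents, with no condition on relatedness.
- Section 11.12.1 requires CRF recording and reporting of "all adverse events (whether or not assessed as serious / related / expected) which the local research team becomes aware of", with database entry within 7 days.

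**Until when.**

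- Section 11 states "ARs will be collected at 6 weeks and 12 weeks" and adds that these are the sole time points. The schedule in section 10.7.1 marks ARs at weeks 0, 6 and 12 and not later.
- Section 10.7.8 says "An assessment of adverse reactions and serious adverse events will be undertaken at each study visit from baseline to the last trial visit". In section 10.7.2, the 24-week list includes ARs and SAEs, and the 52-week list asks for adverse events in general.

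**SAEs and deaths.**

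- Section 11 records SAEs for the whole study.
- Section 11.8 says active monitoring "will be from the period of IMP administration to last dose of IMP and up to their 12 weeks follow-up visit", then requires later SAEs to be reported if the principal investigator learns of them.
- Section 11.11 first asks for any known death within 24 hours, then ends: "Deaths occurring within the active monitoring period described in section 11.8 are reportable".

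**The concern.** These rules decide what enters the database. Two sites that both follow the protocol can record different things for the same child. One enters every non-serious event, another enters related ones only, and a third, reading section 11.2 literally, enters none. One site may ask about reactions at week 24 and another may not.

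Objective 4 compares the arms on adverse reactions and SAEs, alongside laboratory assessments and the pGTI. If the AR data mix several definitions, pooled counts and rates have no single meaning. The trial is open-label. One arm attends a day unit for three days and the other is treated at home for six weeks, so contact with site staff already differs by arm, and a loose recording rule adds to that difference. A statistical analysis plan can discard surplus records, but it cannot restore events that a site was told not to report.

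**Working it through.** No calculation is involved. The check sets the sections against each other by type of event and then by visit.

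**Step 1. Treatment of each event type**

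| Event | Section 11 opening | 11.2 | 11.9 | 11.12.1 |
|---|---|---|---|---|
| Non-serious, related | Reportable | Not reportable as written | Not barred | Record and report |
| Non-serious, unrelated | Not reportable | Not reportable | Do not record, yet injuries and accidents must be recorded | Record and report |
| Serious, unrelated | Reportable | Reportable | Barred if read literally, as SAEs are not exempted | Record and report |
| Serious, related | Reportable | Reportable | Not barred | Record and report |

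Only the last row is free of conflict. For a non-serious unrelated event, no reading satisfies both 11.9 and 11.12.1. For a non-serious related event, which is what an AR count consists of, the conflict is between 11.2 on one side and section 11 and 11.12.1 on the other.

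**Step 2. AR collection points**

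| Source | Weeks | Number | After first dose |
|---|---|---|---|
| Section 11 opening | 6, 12 | 2 | 2 |
| Schedule, 10.7.1 | 0, 6, 12 | 3 | 3 − 1 = 2 |
| Visit lists, 10.7.2 | 0, 6, 12, 24 (adverse events in general at 52) | 4 | 4 − 1 = 3 |
| Section 10.7.8 | 0, 6, 12, 24, 52 | 5 | 5 − 1 = 4 |

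The last column drops week 0. A schedule footnote places baseline procedures before the trial treatment, so no reaction to it can exist then. Section 11 and the schedule therefore agree on what matters: weeks 6 and 12. The conflict lies with 10.7.8 and the later visit lists.

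**Step 3. SAEs and deaths**

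The schedule prompts for SAEs at weeks 0, 6, 12, 24 and 52, at trial completion and at premature discontinuation. Section 11 covers the whole study. Section 11.8 keeps later SAEs reportable. The first sentence of 11.11 sets no time limit, and a death is an SAE under 11.1 and 11.3. No section ends SAE reporting at week 12, but 11.8 and the last sentence of 11.11 can be misread that way.

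**Step 4. Starting point**

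Section 11.8 starts at administration of the trial drug, whereas the schedule and 10.7.8 start at week 0. Oral treatment begins at once (9.1.2) and IV treatment within a week of randomisation (9.1.1). The mismatch can concern only SAEs between randomisation and first dose.

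**The case against.** The strongest defence is that one coherent rule exists and 11.12.1 is the lone outlier. Section 11.2 concerns adverse events, and the opening of section 11 deals with reactions separately. So 11.2 can be taken to mean that, among events that are not reactions, only serious ones are reportable. That fits 11.9 and the schedule. Over-recording under 11.12.1 would then be harmless, because initial reports carry a causality assessment and an onset date, and the analyst can restrict to related events with onset by week 12. The reporting flowchart mentioned in 11.12 is not in the text available here and may make the rule clear. Finally, pGTI is the only outcome that section 6.2 maps to objective 4, and none of this affects it.

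Much of this stands. The charitable reading is available, and restriction by causality and onset date would repair most over-recording. It does not repair under-recording at a site that takes 11.2 literally. Nor does it fully align the visits: a reaction with onset before week 12 that first comes to light at week 24 is captured only where ARs are still sought. Objective 4 itself names adverse reactions, so a comparison on them is intended.

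A reader might go further in three ways that the documents do not support:

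- **That SAE follow-up shrinks from 52 to 12 weeks, or that later deaths go uncollected.** Step 3 shows otherwise. The visit prompts to week 52 also leave no firm basis for assuming that later SAEs will be missed.
- **That the IV arm loses AR follow-up because it may start later.** A reaction cannot precede the dose, and the 12-week visit has a window of ±2 weeks in any case.
- **That the arms are systematically biased against each other.** Randomisation is stratified by site, so a site's reading applies to both arms.

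**Conclusion.** The contradiction is real and stands in the current text, whose amendment table is empty. It concerns non-serious events: which are recorded, and whether ARs are sought after week 12. Its extent is two to five AR collection points (two to four after first dose), and reporting of a non-serious related event that depends on the section followed. The effect on AR counts cannot be given a number, because the protocol states no expected reaction rate and does not say which section sites will use.

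The consequence is a less interpretable AR comparison within objective 4. The primary outcome and the pGTI are unaffected, and SAE reporting continues to week 52. The sections should be corrected, but the fault does not undermine the trial. The conclusion assumes that the flowchart in 11.12 does not override the text. Even if it states a clear rule, the written sections would still need to agree with it.

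**What to change.** Apply one rule throughout, namely the one that section 11 and the schedule already share: ARs and JIA-related uveitis to week 12, and all SAEs including deaths to week 52. Section 11 gives no separate end point for uveitis, so state it explicitly. Then align:

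- **10.7.2**: remove ARs from the 24-week list, and name SAEs instead of adverse events in the 52-week list.
- **10.7.8**: limit AR assessment to week 12 and keep SAE assessment at every visit.
- **11.2**: add ARs and JIA-related uveitis to what is reportable.
- **11.8 and 11.11**: reword so that the active monitoring period cannot be read as a cut-off for SAEs or deaths.
- **11.9**: state that the list of items not to record does not apply to SAEs, and settle whether unrelated injuries and accidents are recorded.
- **11.12.1**: replace the requirement for every adverse event, and its 7-day deadline, with the event classes in section 11.
- **Start of SAE recording**: name one starting point, the same in both arms.

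A short table of event class, start, end, CRF and reporting time would hold all of this. The cost is a wording amendment, a check that the flowchart and CRFs match, and a reminder to sites. No assessments are added.
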